#### **3.5.2 Special Interim Safety Analysis**

A special interim analysis for evaluation of late delayed radiation therapy adverse events (occurring 3 months or more after radiation therapy treatment) will be conducted due to a possible increased incidence of CNS toxicity from delayed radiation necrosis or radiation injury occurring during the first 6 months post RT. After the first 12 subjects treated, including subjects in the Safety Lead-In portion of the trial, have a minimum 24 week overall survival follow-up time, an interim safety analysis for delayed treatment-induced neurotoxicity will be performed. If the incidence of CTCAE grade  $\geq 3$  CNS (neurologic) toxicity deemed possibly, probably, or definitely related to treatment is 33% or higher (i.e., 4 or more subjects of the first 12) in this group, the trial will be halted due to lack of safety.

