#### **4.4 Subject Recruitment and Screening**

All efforts will be made to actively recruit and retain women and members of minority groups and their subpopulations in this study, with the objective of accruing a study population that resembles the age, gender, ethnic and racial composition of the adult U.S. population as closely as possible. The inclusion and exclusion criteria in this study should not have a negative effect on the enrollment of these populations. If any differences are observed in the outcomes of these populations, these results will be reported.

Target enrollment for this study is 24 patients over 18 months. The target accrual goal is 16 patients per year. Patients will be recruited for the study from investigator or sub-investigator clinical practices. Identification of prospective subjects will be conducted by reviewing the medical records of patients in the investigator or sub-investigator's clinical practice and the investigator and sub-investigators will use all efforts to limit its use of protected health information. For study requirements to maintain subject confidentiality and management of study information according to the requirements of the Health Insurance Portability and Accountability Act of 1996 (HIPAA), refer to Section 9.

Informed consent will take place in the investigator or sub-investigator's clinical practice per institutional guidelines when a patient is deemed potentially eligible for participation by the study investigator or sub-investigator. Patients will be asked to give medical information about themselves specific to the inclusion and exclusion criteria outlined in the protocol. Only study investigators will have access to this information. Information collected will include Participant Demographics (address, zip code, sex, race, ethnicity, initials, date of birth), Parameters for eligibility, Parameters for exclusion, and Parameters for stratifications.

The Investigator or Sub-Investigator will:

1. Obtain signed and dated informed consent from the potential subject before any study specific procedures are performed.
2. Determine patient eligibility (See Section 4)
3. Submit registration/eligibility packet to the Research Coordinator at NYUSoM Perlmutter Cancer Center CTO.

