### **5.2.2 Radiation Therapy**

RT must be provided at the study site (NYUSoM).

On Day 8 of Cycle 1 (7 days after initiation of study drugs), all subjects will begin HFRT to a total dose of 45 Gy, given in 15 fractions of 3 Gy.

CONFIDENTIAL

This material is the property of the NYU School of Medicine. Do not disclose or use except as authorized in writing by the study sponsor

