### 6.1.1 **Safety Lead-In**

The first 6 subjects enrolled onto the study will be evaluated as a Safety Lead-In cohort. After all screening, registration and baseline procedures are completed as detailed on the Schedule of Events (Appendix 1), subjects will begin the study regimen.

On Day 1 of Cycle 1, subjects will be administered one dose of nivolumab 3 mg/kg IV and one dose of ipilimumab 1 mg/kg IV.

On Day 8 of Cycle 1, subjects will be administered RT to a total dose of 45 Gy, given in 15 fractions of 3 Gy.

CONFIDENTIAL

This material is the property of the NYU School of Medicine. Do not disclose or use except as authorized in writing by the study sponsor

On Day 15 of Cycle 1, nivolumab 3 mg/kg IV will be administered, and subsequently continue once every 2 weeks.

Ipilimumab 1 mg/kg IV will continue once every 6 weeks after the first ipilimumab dose on Cycle 1 Day 1.

The **DLT evaluation period** will be defined as the **first 53 days** on study. The DLT period will start with the first infusion (**Day 1**) and will **end 4 weeks following the final day of radiation**, ie, **Days 1-53**.

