### 6.1.2 Main Study Cohort

Following completion of the Safety Lead-In, subjects meeting eligibility criteria will be enrolled onto the phase II portion of the study (Main Study Cohort). The Phase II trial is a one-stage design phase II trial with analyses for safety (see Section 7 for Statistical Methods). A total of 24 patients are anticipated to be treated in the Main Study Cohort.

After all screening, registration and baseline procedures have been completed as detailed on the **Schedule of Events (Appendix 1)**, subjects will begin study treatment. If the initial doses of nivolumab and ipilimumab are found to be safe, subjects in the phase II portion of the study will be treated as below:

On C1D1, subjects will be administered one dose of nivolumab 3 mg/kg IV and one dose of ipilimumab 1 mg/kg IV.

On C1D8, subjects will be administered RT to a total dose of 45 Gy, given in 15 fractions of 3 Gy on consecutive days (i.e., 5 days per week).

On C1D15, subjects will receive nivolumab 3 mg/kg. Thereafter, nivolumab 3 mg/kg IV will continue once every 2 weeks.

On C1D29, subjects will receive ipilimumab 1 mg/kg IV. Thereafter, ipilimumab 1 mg/kg IV will continue once every 6 weeks.

Nivolumab and ipilimumab administration will continue for up to 2 years or until disease progression, death, intolerable toxicity, or the subject discontinues study therapy as per any of the protocol subject withdrawal guidelines. Subjects who are discontinued from study therapy will enter the post-study follow-up phase of the study.

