### 7.2.2 Main Study Cohort - Phase II trial design

A single-stage design will be utilized to estimate overall survival, with a hypothesized 1yr-OS of 60%= $H_1$  and 35%= $H_0$ . We will enroll 24 patients; this design has a two-sided Type I error of 0.05 and a power of 80%.

For endpoint analyses, one year will be defined as 48 weeks (8 cycles) and two years will be defined as 96 weeks (16 cycles). Patients will be evaluated for radiographic responses by conventional contrast enhanced MRI every 8 weeks. Radiographic response assessments will be determined using RANO criteria for GBM.

1yr-OS and radiographic response rates will be estimated with exact 95% confidence intervals; with 24 patients, a 95% CI will be no more than 0.4 units wide. OS will be determined from the time of treatment initiation until the time of death due to any cause, with OS being censored at last follow-up if the patient remained alive. Patients who were last known to be alive and progression-free will be censored at the latest disease assessment. The Kaplan–Meier curves will be used to summarize OS and to estimate the medians.

PFS is defined as the time between treatment initiation and first occurrence of disease progression or death, and will be censored at last follow-up if the patient remained alive without disease progression. PFS is defined as the time from the first dose of study treatment to the earlier of disease progression or death due to any cause. Patients who initiate alternate anticancer therapy in the absence of documented progression will be censored at the latest disease assessment prior to initiation of such therapy. Patients with no post-baseline disease assessments will be censored at the Cycle 1 Dose 1 date unless death occurred prior to the first planned assessment (in which case the death will be considered a PFS event). The Kaplan–Meier curves will be used to summarize PFS and to estimate the medians.

Overall response rate (ORR) is defined as the proportion of patients who achieve best overall response of complete or partial response at any time after initiation of study treatment (prior to initiation of alternate anticancer treatment). Duration of response is defined as the number of months from the time criteria are first met for either CR or PR, until the first date that PD is objectively documented. The duration of objective response will be summarized descriptively using the Kaplan-Meier method.

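### The halt on four CNS events among the first 12 subjects applies only at one scheduled look, and that look's 24-week clock runs from first dose although its stated purpose is the first 6 months after radiotherapy

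*Combined protocol and SAP*

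**What the plan says.** Section 3.5.2 sets up one special interim analysis for late delayed radiation events, those "occurring 3 months or more after radiation therapy treatment". It gives the reason as "due to a possible increased incidence of CNS toxicity from delayed radiation necrosis or radiation injury occurring during the first 6 months post RT". The analysis is done once the first 12 treated subjects, lead-in included, "have a minimum 24 week overall survival follow-up time, an interim safety analysis for delayed treatment-induced neurotoxicity will be performed". If 4 or more of those 12 have CNS toxicity of grade 3 or higher that is at least possibly related to treatment, the trial is halted.

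Section 3.5.2 gives no start date for the 24 weeks. Section 7.2.2 does so for survival: "OS will be determined from the time of treatment initiation until the time of death due to any cause". Radiotherapy comes later. Section 5.2.2 states: "On Day 8 of Cycle 1 (7 days after initiation of study drugs), all subjects will begin HFRT". Section 6.1.2 gives 15 fractions at five per week. On pace, Section 4.4 says: "The target accrual goal is 16 patients per year".

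**The concern.** Two things in Section 3.5.2 do not fit its purpose.

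First, the risk period is counted from radiotherapy and the trigger from the first dose of study drug. The most recently treated of the 12 subjects can therefore reach the look before 6 months after radiotherapy, and the rule could miss late events in that subject.

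Second, the halt is attached to the scheduled analysis and to nothing else. Once a fourth qualifying event has been confirmed among the first 12, waiting cannot change the result. The section still requires no action until the look and does not pause accrual in the meantime. At stake is how many patients start a regimen that the plan's own criterion has already failed.

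**Working it through.** **Threshold.** 4/12 = 33.3% and 3/12 = 25%, so 4 is the smallest count that meets the stated 33%. The plan's figure reproduces.

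**Minimum follow-up after radiotherapy, main cohort.**
- Trigger: 24 × 7 = 168 days from first dose.
- Last fraction: starting on Day 8 at five per week, 15 fractions end on Day 26, which is 25 days after first dose.
- Cross-check: Section 6.1.1 gives a window of Days 1-53 said to "end 4 weeks following the final day of radiation"; 53 − 28 = Day 25, within one day. (Other passages give a different length for that window; it is used here only to date the last fraction.)
- 168 − 25 = 143 days, or 143/30.44 = 4.7 months. If radiotherapy runs to Day 35 (Section 5.2.2.2 allows 3-4 weeks), 168 − 34 = 134 days, or 4.4 months.
- Shortfall against 182 days: 182 − 143 = 39 days. Of days 91-182, subject 12 contributes (143 − 91)/91 = 57%.

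**All 12 subjects.** At 16 per year, evenly spaced, subjects start 365/16 = 22.8 days apart. Follow-up after radiotherapy at the trigger is 143 days for subject 12, 143 + 22.8 = 166 for subject 11, 189 for subject 10, and longer for the rest. Ten of 12 are past 182 days. Mean coverage of days 91-182 is (10 × 1 + 0.82 + 0.57)/12 = 95%.

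**Effect on the rule** (assumed true 6-month rate of 40%).
- Full follow-up of all 12: P(4 or more of 12) = 0.775.
- Constant hazard over 6 months: the chance that an event is seen is 1 − 0.6^(143/182) = 0.331 for subject 12, 1 − 0.6^(166/182) = 0.372 for subject 11, and 0.40 for the other ten. P(4 or more) = 0.757.
- All events spread evenly over months 3-6: 0.40 × 52/91 = 0.229 for subject 12, 0.40 × 75/91 = 0.33 for subject 11, and 0.40 for the rest. P(4 or more) = 0.73.
- All 12 at the minimum, constant hazard: P(4 or more) = 0.60. This would need all 12 to start together.

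**Patients enrolled while waiting.** 16 × 24/52 = 7.4 in the 24 weeks between the twelfth subject's start and the look.

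**Would another rule act at 4 of 12?** The Bayesian boundary at 12 patients in Section 3.5.1 is 7. With the Beta(2,3) prior, 4 of 12 gives P(rate > 0.40) = 0.33 and P(rate > 0.30) = 0.66, against a listed 0.86 at the boundary. Four CNS events alone reach a boundary only if they cluster early (2 of the first 3, or 4 of the first 6), and even then termination is only considered. The lead-in toxicity window closes by Day 53 at the latest, before a late event can begin. Extra committee reviews (Section 8.6.1) are optional and have no numeric CNS trigger.

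**Surgical Study Cohort, if its subjects count.** Section 6.1.3 puts surgery 14 days and radiotherapy 35 days after first dose. The last fraction is then at 35 + 18 = 53 days, and 168 − 53 = 115 days (3.8 months).

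**The case against.** The strongest reply is that 24 weeks is a minimum. Ten of 12 subjects pass 6 months after radiotherapy at planned accrual, and the staggered start and enrolment halts of the lead-in lengthen follow-up for the earliest subjects further. The halt count also takes in any qualifying CNS event, not only those in months 3-6. Section 7.2.2 defines a year as 48 weeks, so 24 weeks is the plan's own half-year. A later look is not free either: 39 days at 16 per year is 16 × 39/365 = 1.7, so about 2 more patients would be enrolled before it. All of this stands, and it makes the timing mismatch minor. It does not remove it, because the clock still starts before radiotherapy.

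On the halt, Section 3.5.2 does not forbid earlier action, serious events go to the committee (Section 8.4), and extra reviews can follow (Section 8.6.1). That also stands. The gap is a missing binding trigger; accrual is not unmonitored.

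A reader might infer that this is the plan's only protection against overlapping toxicity. Section 1.3.3 names the Safety Lead-In as well, and its toxicity definition includes neurological events. The interim is the only rule aimed at late events. A reader might also infer that passing the look declares the regimen acceptable. The rule only halts; other toxicity monitoring continues.

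**Conclusion.** The point holds at moderate severity. The guaranteed minimum after radiotherapy is about 143 days, against a stated purpose of 6 months. The cost to the rule at planned accrual is small: 0.775 to 0.757, or 0.73 if every event is late. These figures assume a 40% true rate, even spacing at 16 per year and survival time counted from first dose; faster accrual would make the loss larger. The value of 0.60, with all 12 at minimum follow-up, is a limit and should not be read as the expected loss.

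The missing action at the fourth event matters more. The outcome is then fixed, no other rule binds, and up to about 7 further patients could enrol if events come early in the wait. The number depends on when the fourth event falls.

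The 115-day figure is conditional. Section 3.5.2 does not say whether Surgical Study Cohort subjects are among the 12, and the figure applies only if the latest subject is one of them.

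**What to change.** Amend Section 3.5.2 in three places.

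1. Keep the threshold of 4 of the first 12. State that the count is kept continuously and that the halt applies as soon as the fourth qualifying event among those 12 is confirmed, without waiting for the scheduled analysis.
2. Reconcile the purpose with the clock. Either measure follow-up from the last fraction (or to death if earlier), or keep the 24-week look and go on counting the first 12 against the same threshold until each reaches 6 months after radiotherapy.
3. State whether Surgical Study Cohort subjects count among the first 12, and how a death before the minimum follow-up is handled.

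The cost is a paragraph of amendment text and a running tally. Under the first option in item 2 the formal look moves about 39 days later, with about 2 more patients enrolled before it. The continuous count offsets this, because it can only bring a halt forward. The second option leaves the look where it is.

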## **4 Subject Selection**

### **4.1 Inclusion Criteria**

1. Male or female subjects aged  $\geq 18$  years.
2. Histopathological evidence of glioblastoma or gliosarcoma, WHO grade IV.
3. Tumor *MGMT* promoter DNA not methylated (i.e., unmethylated) by central testing.

CONFIDENTIAL

This material is the property of the NYU School of Medicine. Do not disclose or use except as authorized in writing by the study sponsor

4. There will be two study cohorts:
  - **Main Study Cohort:** Maximal tumor diameter of 6.6 cm or less. Patients with multifocal tumors are allowed if the sum of the maximal tumor diameters does not exceed 6.6 cm. Note, the maximal tumor diameter for the first 3 subjects enrolled will be 5 cm.
  - **Surgical Study Cohort:** Patients who received tumor biopsy or subtotal tumor resection and are amenable to a second tumor resection with expected post-operative tumor diameter of  $\leq 6$  cm (PTV of  $\leq 150$  cm $^3$ )
5. Subjects must not have received any prior standard or investigational anti-tumor therapy other than surgery and must not intend to receive any standard or investigational anti-tumor therapy other than the study regimen.
6. Karnofsky performance status (Appendix 2) of  $\geq 60$ .
7. Availability of a paraffin-embedded or frozen tumor-tissue block with a minimum of 1 cm $^2$  of tumor surface area, or 20 unstained slides from the glioblastoma tissue specimen if a tumor block cannot be submitted. . For Surgical Study Cohort: availability of pre- and post-operative tumor tissue is required.
8. Subjects must start study agent within 6 weeks from the first diagnostic surgery for glioblastoma.
9. Begin of Study Treatment:
  - An interval of at least 2 weeks for surgical resection and 1 week for stereotactic biopsy from the start of study treatment. **Main Study Cohort:** Subjects must start study agents no sooner than 2 weeks from last surgical resection and 1 week from stereotactic biopsy.
  - **Surgical Study Cohort:** Subjects must receive 1st dose of study agents 2 weeks prior to tumor re-resection and must resume study agents no sooner than 2 weeks from date of tumor re-resection.
10. A contrast-enhanced MRI must be obtained within 21 days of the first dose of study treatment.
11. Adequate hematologic, hepatic, and renal function defined by
  - a. White blood cell count  $\geq 2.0 \times 10^9/L$
  - b. Absolute neutrophil count  $\geq 1.5 \times 10^9/L$
  - c. Platelet count  $\geq 100 \times 10^9/L$
  - d. Hemoglobin  $> 9$  g/dL
  - e. Serum creatinine  $\leq 1.5 \times$  upper limit of normal (ULN) or creatinine clearance (CrCl)  $\geq 40$  mL/min according to the Cockcroft-Gault formula or local institutional standard method
  - f. Aspartate aminotransferase (AST) and alanine aminotransferase (ALT)  $\leq 3 \times$  ULN
  - g. Total bilirubin  $\leq 1.5 \times$  ULN (except subjects with Gilbert Syndrome, who can have total bilirubin  $< 3.0$  mg/dL)
35. Women of child-bearing potential (WOCBP) and men able to father a child must agree to use highly effective contraception (any contraceptive method with a failure rate of less than 1% per year) while on study drug and for 23 weeks (for women) or 31 weeks (for men) after the last dose of study drug.
  - a. WOCBP must have a negative serum or urine pregnancy test within 24 hours of initiation of study drug.
  - b. WOCBP is defined as any female who has experienced menarche and who has not undergone surgical sterilization (hysterectomy or bilateral oophorectomy) or who is not postmenopausal. Menopause is defined clinically as 12 months of amenorrhea in a woman over 45 in the absence of other biological or physiological causes. In addition,

CONFIDENTIAL

This material is the property of the NYU School of Medicine. Do not disclose or use except as authorized in writing by the study sponsor

women under the age of 55 must have a documented serum follicle stimulating hormone (FSH) level less than 40 mIU/mL to be defined as post-menopausal.

- c. WOCBP receiving nivolumab will be instructed to adhere to contraception for a period of 23 weeks after the last dose of investigational product. Men receiving nivolumab and who are sexually active with WOCBP will be instructed to adhere to contraception for a period of 31 weeks after the last dose of investigational product. These durations have been calculated using the upper limit of the half-life for nivolumab (25 days) and are based on the protocol requirement that WOCBP use contraception for 5 half-lives plus 30 days and men who are sexually active with WOCBP use contraception for 5 half-lives plus 90 days.
- d. Highly effective contraceptive measures include: stable use of oral contraceptives such as combined estrogen and progestogen and progestogen only hormonal contraception or other prescription pharmaceutical contraceptives for 2 or more menstrual cycles prior to screening; intrauterine device [IUD]; intrauterine hormone-releasing system (IUS); bilateral tubal ligation; vasectomy and sexual abstinence.
- e. Contraception is not required for men with documented vasectomy.
- f. Pregnancy testing and contraception are not required for women with documented hysterectomy or tubal ligation.
- g. Women must not be breastfeeding.

36. Willing to and capable of providing written informed consent prior to any study related procedures.

37. Ability and willingness to comply with all study requirements, including scheduled visits, treatment plans, laboratory tests, and other study-related procedures.

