  - c. Platelet count ≥ 100 × 10^9/L
  - d. Hemoglobin > 9 g/dL
  - e. Serum creatinine ≤ 1.5 × upper limit of normal (ULN) or creatinine clearance (CrCl) ≥ 40 mL/min according to the Cockcroft-Gault formula or local institutional standard method
  - f. Aspartate aminotransferase (AST) and alanine aminotransferase (ALT) ≤ 3 × ULN
  - g. Total bilirubin ≤ 1.5 × ULN (except subjects with Gilbert Syndrome, who can have total bilirubin < 3.0 mg/dL)
12. Women of child-bearing potential (WOCBP) and men able to father a child must agree to use highly effective contraception (any contraceptive method with a failure rate of less than 1% per year) while on study drug and for 23 weeks (for women) or 31 weeks (for men) after the last dose of study drug.
  - a. WOCBP must have a negative serum or urine pregnancy test within 24 hours of initiation of study drug.

CONFIDENTIAL

This material is the property of the NYU School of Medicine. Do not disclose or use except as authorized in writing by the study sponsor

- b. WOCBP is defined as any female who has experienced menarche and who has not undergone surgical sterilization (hysterectomy or bilateral oophorectomy) or who is not postmenopausal. Menopause is defined clinically as 12 months of amenorrhea in a woman over 45 in the absence of other biological or physiological causes. In addition, women under the age of 55 must have a documented serum follicle stimulating hormone (FSH) level less than 40 mIU/mL to be defined as post-menopausal.
- c. WOCBP receiving nivolumab will be instructed to adhere to contraception for a period of 23 weeks after the last dose of investigational product. Men receiving nivolumab and who are sexually active with WOCBP will be instructed to adhere to contraception for a period of 31 weeks after the last dose of investigational product. These durations have been calculated using the upper limit of the half-life for nivolumab (25 days) and are based on the protocol requirement that WOCBP use contraception for 5 half-lives plus 30 days and men who are sexually active with WOCBP use contraception for 5 half-lives plus 90 days.

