#### 1.2.1.2 Nonclinical Studies of Nivolumab

Nivolumab has been shown to bind specifically to the human PD-1 receptor and not to related members of the CD28 family. Nivolumab inhibits the interaction of PD-1 with its ligands, PD-L1 and PD-L2, resulting in enhanced T-cell proliferation and interferon-gamma (IFN- $\gamma$ ) release *in vitro*. Nivolumab binds with high affinity to activated human T-cells expressing cell surface PD-1 and to cynomolgus monkey PD-1. In a mixed lymphocyte reaction (MLR), nivolumab promoted a reproducible concentration-dependent enhancement of IFN- $\gamma$  release.

In intravenous (IV) repeat-dose toxicology studies in cynomolgus monkeys, nivolumab was well tolerated at doses up to 50 mg/kg, administered weekly for 5 weeks, and at doses up to 50 mg/kg, administered

CONFIDENTIAL

This material is the property of the NYU School of Medicine. Do not disclose or use except as authorized in writing by the study sponsor

twice weekly for 27 doses. While nivolumab alone was well tolerated in cynomolgus monkeys, combination studies have highlighted the potential for enhanced toxicity when combined with other immunostimulatory agents.

In addition, an enhanced pre- and postnatal development (ePPND) study in pregnant cynomolgus monkeys with nivolumab was conducted. Administration of nivolumab at up to 50 mg/kg 2QW was well tolerated by pregnant monkeys; however, nivolumab was determined to be a selective developmental toxicant when administered from the period of organogenesis to parturition at  $\geq 10$  mg/kg (area under the concentration-time curve [AUC] from time zero to 168 hours [AUC(0 168 h)] 117,000  $\mu$ g•h/mL). Specifically, increased developmental mortality (including late gestational fetal losses and extreme prematurity with associated neonatal mortality) was noted in the absence of overt maternal toxicity. There were no nivolumab-related changes in surviving infants tested throughout the 6-month postnatal period. Although the cause of these pregnancy failures was undetermined, nivolumab-related effects on pregnancy maintenance are consistent with the established role of PD-L1 in maintaining fetomaternal tolerance in mice.

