## 6.4 Study Procedures Main Study Cohort

### 6.4.1 Cycle 1, Day 1 (C1D1)

**One treatment cycle will be defined as 42 days**, corresponding to 3 doses of nivolumab (administered every 2 weeks) and one dose of ipilimumab (administered every 6 weeks). If nivolumab and ipilimumab dosing is delayed, the cycle count should be interrupted.

After screening and registration procedures, the subject will have all of the C1D1 Safety Procedures detailed below performed prior to initiating study treatment (first dose of nivolumab and ipilimumab),

CONFIDENTIAL

This material is the property of the NYU School of Medicine. Do not disclose or use except as authorized in writing by the study sponsor

within 3 days (except MRI procedures, which can be performed within 21 days) of treatment initiation. Evaluations performed at screening that fall within 3 days of treatment initiation will not need to be repeated. The baseline labs do not need to re-meet the specific eligibility criteria, only meet criteria for dosing.

- Adverse event assessment
- Concomitant medication collection
- Complete physical exam, including neurological exam, and KPS assessment
- Vital signs: When scheduled at the same visit as other procedures, vital signs should be measured prior to clinical laboratory assessments or research blood sample collection.
  - Weight (can be taken within 3 days of scheduled ipilimumab administration), temperature, resting blood pressure, pulse and respiration rate.
  - For C1D1, the following vital signs will be collected prior to treatment, at the end of the infusions, and every 30 minutes for the first hour post-infusion (all timepoints  $\pm 10$  minutes):
    - Temperature, resting blood pressure, pulse and respiration rate
- Serum chemistry: sodium, potassium, chloride, bicarbonate, calcium, magnesium, phosphorous, glucose, albumin, creatinine, blood urea nitrogen (BUN), uric acid, ALT, AST, total bilirubin, direct and/or indirect bilirubin, alkaline phosphatase (ALP), lactate dehydrogenase (LDH), amylase, and lipase.
- Hematology: WBC count, 3-cell differential (ANC, monocyte count, lymphocyte count), hemoglobin, hematocrit, and platelet count
- T cell subsets (CD3, CD4, and CD8 counts)
- Thyroid stimulating hormone (TSH), free T4
- Pregnancy test (urine or serum  $\beta$ -HCG) for women of child-bearing potential
- Contrast-enhanced brain MRI (within 21 days of study drug initiation)
- Research MRI (sodium MRI) within 21 days of study drug initiation.

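### The FSH condition for classing women under 55 as post-menopausal appears reversed, in both the synopsis and Section 4.1

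*Combined protocol and SAP*

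**What the plan says.** Synopsis inclusion criterion 12b and item (b) of the contraception criterion in Section 4.1 define menopause in the same way. The clinical condition comes first: "Menopause is defined clinically as 12 months of amenorrhea in a woman over 45 in the absence of other biological or physiological causes". A further condition is then added by age. The synopsis states that "women under the age of 55 must have a documented serum follicle stimulating hormone (FSH) level less than 40 mIU/mL to be defined as post-menopausal", and Section 4.1 repeats it with the same cut-off and direction: women under 55 "must have a documented serum follicle stimulating hormone (FSH) level less than 40 mIU/mL to be defined as post-menopausal".

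Both places define WOCBP as a woman past menarche "who has not undergone surgical sterilization (hysterectomy or bilateral oophorectomy) or who is not postmenopausal". The consequences hang on that status. WOCBP "must agree to use highly effective contraception" on study drug and, for women, for 23 weeks after the last dose. Item (a) adds that "WOCBP must have a negative serum or urine pregnancy test within 24 hours of initiation of study drug". Later pregnancy tests, at treatment visits, at end of treatment and at the 30- and 90-day visits, are likewise limited to women of child-bearing potential.

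On timing, Section 6.4.1 lists the pregnancy test among procedures that may be done up to 3 days before the first dose, and says: "Evaluations performed at screening that fall within 3 days of treatment initiation will not need to be repeated". Section 6.5.1 and footnote 12 of both schedules of events say the same.

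**The concern.** The FSH clause is an additional check on women who already meet the clinical definition but are still under 55. Such a check should separate women whose ovarian function has ceased from those in whom it may persist. A low FSH does not confirm menopause and a high one supports it. As worded, the clause accepts the low result and rejects the high one.

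A woman wrongly classed as post-menopausal at entry would have no contraception requirement, no pregnancy test before the first dose and no scheduled test afterwards. The protocol gives its own reason for caution: Section 1.2.1.2 reports that "nivolumab was determined to be a selective developmental toxicant", from a study in pregnant cynomolgus monkeys at 10 mg/kg or more, dosed from organogenesis to parturition. The opposite error, keeping a post-menopausal woman in the WOCBP group, costs unneeded tests and contraception but creates no fetal risk.

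**Working it through.** No sample size, power or error rate is involved, so this is a check of text and logic.

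**1. Is the wording an isolated slip or an extraction fault?** The direction is spelled out in words, not as a symbol, and is identical in the synopsis and Section 4.1. No other section states the opposite or corrects it.

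**2. Who is reached by the FSH clause?** The clinical definition applies only above age 45, and the FSH clause only below 55. Take a non-sterilized woman with 12 months of amenorrhea and no other cause, and read the WOCBP definition by its evident intent (either sterilization or menopause removes the status):

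| Age | Documented FSH | Class as written |
|---|---|---|
| 45 or under | any | WOCBP |
| over 45, under 55 | below 40 mIU/mL | post-menopausal, exempt |
| over 45, under 55 | 40 mIU/mL or above | WOCBP |
| over 45, under 55 | none on file | WOCBP |
| 55 or over | not needed | post-menopausal, exempt |

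Only rows two and three are inverted. For illustration, a 48-year-old with FSH 10 mIU/mL is exempt, while a 52-year-old with FSH 80 mIU/mL is not.

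**3. What does the 'or' do?** Read literally, the definition is (not sterilized) or (not post-menopausal). A non-sterilized woman satisfies the first limb whatever her FSH, so she stays WOCBP and the menopause clause has no effect on her. The same literal reading would keep a woman with a hysterectomy who is not post-menopausal as WOCBP, whereas item (f) of the criterion frees women with a documented hysterectomy or tubal ligation from testing and contraception. Item (f) and the detailed menopause definition both point to the intended reading, but the text does not state it.

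**4. Is FSH collected?** It is absent from the screening laboratories in Section 6.3 and from both schedules of events. The criterion depends on a value that no procedure generates. A wrongful exemption therefore needs a low FSH already on file or obtained outside the schedule.

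**5. How many women?** The documents give no age or sex distribution, so no count can be derived. The ceiling is 24 + 16 = 40 subjects of both sexes and all adult ages. Rows two and three can cover only a few of them.

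**6. Pregnancy-test window.** Item (a) allows 24 hours. The visit rules allow 3 days, or 3 × 24 = 72 hours. A negative test two days before dosing satisfies Sections 6.4.1 and 6.5.1 and fails item (a). A test within 24 hours satisfies both.

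**The case against.** The case against a broad reading is strong, and most of it stands.

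- A reader might infer that the criterion, applied literally, exempts fertile women. It does not: on the literal 'or', no non-sterilized woman is exempted by her FSH. The exemption arises only on the intended reading.
- A reader might infer that every woman aged over 45 and under 55 with amenorrhea is misclassified. The clinical condition already excludes amenorrhea with another recognized cause, exemption needs a documented FSH that is not scheduled, and women with hysterectomy or tubal ligation are exempt under a separate item.
- A reader might infer that an exempted woman falls outside all pregnancy safeguards. Discontinuation on pregnancy (Section 6.9), pregnancy follow-up (Section 8.1) and reporting (Section 8.4.1) are not limited to WOCBP. What she loses is prevention and scheduled detection.
- A reader might infer that the 3-day allowance means women who fail criterion (a) would be dosed. Section 4.5.1 requires all criteria to be met at enrollment, and the 24-hour rule is the more specific one. A site relying on the allowance could breach it; the text does not make it do so.
- The documents do not say why the FSH clause was added or which way FSH moves at menopause. The two definitions agree with each other, so this is not an internal contradiction.

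None of this makes the direction right. The clause still names the result that fails to confirm menopause as the one that confirms it.

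**Conclusion.** The concern holds in a narrow form. The FSH condition in synopsis criterion 12b and Section 4.1(b) appears reversed, most likely through a drafting error, and it sits in an operative eligibility rule that controls contraception and pregnancy testing. The conclusion rests on two assumptions: that FSH rises when ovarian function ceases, which is general physiology and not a statement in the documents, and that either sterilization or menopause was meant to remove WOCBP status. If the literal 'or' governs instead, nobody is wrongly exempted, but the menopause definition then does nothing for non-sterilized women and the text still needs correcting.

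The reach is small and the matter is one of participant safety and eligibility. It does not bear on the endpoints or their analysis. The conflict between the 24-hour and 3-day windows is real but secondary.

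**What to change.** The sponsor should:

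1. Correct the direction of the FSH inequality in synopsis 12b and Section 4.1(b), so that the result confirms menopause and does not contradict it. The clinical content of the criterion is for the sponsor to settle.
2. Reword the 'or' in the WOCBP definition so that it is clear whether sterilization or menopause alone removes the status, consistently with item (f).
3. Reconcile the criterion with Section 6.3 and both schedules of events, which contain no FSH test.
4. Re-check the classification of any enrolled women over 45 and under 55.
5. Reconcile item (a) with Sections 6.4.1 and 6.5.1 and footnote 12 of both schedules, so that one pregnancy-test window applies.

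The cost is a wording change in two places, one clarified definition, one reconciled window, a file check on a handful of women and possibly a few more pregnancy or FSH tests. Dose, treatment schedule, sample size and analysis do not change.
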